2. STUDY OBJECTIVES AND ENDPOINTS

2.1. Primary

The primary objectives of the study are:

- To determine the effect of once daily (QD) TVB-2640 for 12 weeks versus placebo on the change in hepatic fat fraction by proton density fat fraction by magnetic resonance imaging (MRI-PDFF) from baseline in subjects with NASH.
- To determine the safety of QD TVB-2640 versus placebo in subjects with NASH, including the effects on alanine aminotransferase (ALT) and aspartate aminotransferase (AST).

2.2. Secondary

The secondary objective is:

- To determine the effect of QD TVB-2640 for 12 weeks versus placebo in subjects with NASH on:
 - Lipid and lipoprotein parameters, including low-density lipoprotein cholesterol (LDL-C), non-LDL-C, high-density lipoprotein cholesterol (HDL-C), non-HDL-C, total cholesterol, triglycerides (TG), apolipoprotein B (ApoB), and lipoprotein(a) (Lp[a]) particles.
 - NASH and fibrosis biomarkers including cytokeratin-18 (CK-18), fibrosis-4 (FIB-4), and enhanced liver function (ELF) or FIBROspect 2 or ProC3 test.
 - Eicosanoid panel.

2.3. Exploratory

The exploratory objectives are:

- To determine the effect of QD TVB-2640 for 12 weeks versus placebo in subjects with NASH on clinical measures, including:
 - Liver fibrosis, as determined by vibration-controlled transient elastography (VCTE).

Sponsor: Sagimet Biosciences

Protocol Number: 3V2640-CLIN-005

Version and Date: Final Version 1, 02June2020

- Metabolic parameters, including fasting glucose, insulin, homeostatic model assessment insulin resistance (HOMA2-IR), glycated hemoglobin (HbA1c), non-esterified fatty acid (NEFA), adipose tissue insulin resistance (adipo-IR), adiponectin, resistin, Interleukin 6 (IL-6), and gamma-glutamyl transpeptidase (GGT).
- Anthropometric parameters, including weight, waist and hip circumference, waist-hip ratio, and blood pressure.
- Lipidomic analyses for de novo lipogenesis (DNL).
- Explore the relationship of plasma drug exposure to changes in efficacy and safety biomarkers.
- Explore possible relationships between genomic markers of NASH and responses to treatment.

3. STUDY DESIGN

3.1. Study Design and Population

This is a multi-center, randomized, single-blind, placebo-controlled, dose-escalation study to evaluate the safety and efficacy of TVB-2640 in subjects with NASH. Male and female subjects aged ≥ 18 years with either biopsy-proven NASH within 2 years before randomization and MRI-PDFF $\geq 8\%$ or, if prior liver biopsy was not performed or results are not available, magnetic resonance elastography (MRE) ≥ 2.5 kpa and MRI-PDFF $\geq 8\%$ during screening are planned to be enrolled. Approximately 117 subjects will be enrolled and randomized, with at least 90 subjects enrolled in the US and approximately 27 subjects enrolled in China (18 active and 9 placebo). In the US, subjects will be enrolled and randomized to achieve 90 evaluable subjects (30 active and 15 placebo in each of 2 dose cohorts). The 50 mg cohort will enroll and randomize approximately 27 additional subjects from China. A subject is defined as evaluable if they receive study drug for at least 8 weeks and have a baseline and at least 1 post-baseline MRI-PDFF assessment on or after Week 8.

Subjects will receive TVB-2640 or placebo QD orally (PO) for 12 weeks. During the 12-week Treatment period, subjects are to attend study center visits on Days 1 and 2, and Weeks 2, 4, 8, and 12. After completion of the 12-week Treatment period, subjects are to attend a Follow-up visit at Week 16 for post-treatment safety and efficacy assessments.

All subjects must complete the 12-week treatment period at the 25 mg dose level, with review of all safety data and written approval by the Safety Review Committee (SRC) and reviewed by the Food and Drug Administration (FDA) before enrollment and treatment of subjects at the 50 mg dose level may commence.

Due to the impact of COVID-19, several subjects were unable to have their Week 12 end of treatment visit performed within the protocol defined window. These subjects received extended dosing of study product and will have their end of treatment visit collected more than 12 weeks post first dose of study product, with allowable ranges between Week 11 and Week 16. Study

Sponsor: Sagimet Biosciences
Protocol Number: 3V2640-CLIN-005
Version and Date: Final Version 1, 02June2020

drug was not permitted to be continued for more than 16 weeks. For these subjects, the End of Study Visit was scheduled for 4 weeks after the last dose of study drug. For purposes of consistent terminology in context of the COVID changes, the following terminology will be used,

End of Treatment Visit: Visit performed following the end of study treatment. This will be the Week 12 visit for subjects who completed the treatment period as planned. For subjects who entered extended dosing, the visit will be performed on or prior to Week 16. For subjects who received less than 12 weeks of study treatment, the visit will be prior to the scheduled Week 12 visit.

End of Study Visit: Visit corresponding to 4 weeks after the end of treatment visit. This will be the Week 16 visit for subjects who completed the treatment period as planned.

3.2. Randomization and Blinding

Subjects who are candidates for enrollment into the study will be assigned a sequential and unique subject number by the Investigator after the subject has provided written informed consent. Once a subject number has been assigned, it cannot be reused.

Subjects who have provided written informed consent will be evaluated for eligibility by the Investigator to ensure that the entry criteria (see Protocol Sections 8.2 and 8.3) have been satisfied and that the subjects is eligible for participation in this clinical study.

Two TVB-2640 dose levels are planned to be evaluated in a sequential fashion: 25 mg and, if study suspension criteria are not met at the 25 mg dose level (see Protocol Section 7.2), 50 mg. At each dose level, subjects will be randomly assigned to TVB-2640 or placebo at a 2:1 ratio, with randomization stratified by type 2 diabetes mellitus (DM) status. The 50 mg dose level will also be stratified by country:

- 25 mg dose level: TVB-2640 (Planned N=30) and Placebo (Planned N=15)
- 50 mg dose level: US: TVB-2640 (Planned N=30) and Placebo (Planned N=15); China: TVB-2640 (Planned N=18) and Placebo (Planned N=9); Total: TVB-2640 (Planned N=48) and Placebo (Planned N=24)

Randomization will be done via Interactive Web Response System (IWRS). Subjects are to receive their first study drug dose on Day 1 within 24 hours after randomization.

At both dose levels, subjects will receive TVB-2640 or placebo QD PO for 12 weeks.

Study drug will be dispensed to subjects in a single-blinded fashion. All other study personnel, with the exception of personnel conducting/interpreting imaging studies (see Protocol Section 11.1) at each study center, will be unblinded to the subject's treatment assignment.

3.3. Sample Size Considerations

The sample size is based on a fixed-sequence strategy which tests for a treatment difference in the primary endpoint (percent change at Week 12 in liver fat from baseline as determined by

MRI-PDFF) between each TVB-2640 dose group versus placebo. The fixed-sequence strategy will start with the highest dose group comparison. If statistically significant, then testing will proceed to the low dose group comparison. Each TVB-2640 dose group will be compared to the pooled placebo group using an F-test test from an analysis of covariance (ANCOVA) model with fixed effects for the stratification factor (diabetes presence/absence) and treatment group (i.e., TVB-2640 dose groups and pooled placebo) and with the baseline MRI-PDFF value as a covariate. Since the primary efficacy endpoint may not be normally distributed, the non-parametric Wilcoxon rank-sum test is conservatively used, instead of the F-test, for power calculations.

The sample size is based on a conservative assumption that the primary analysis is going to be performed in the US population only, resulting in 30 evaluable subjects in the placebo group, and 30 evaluable subjects in each of the TVB-2640 dose levels. Based on Patel (2016), it is conservatively assumed that the primary endpoint has a standard deviation of 30. Power calculations assume the primary endpoint is lognormally distributed with a standard deviation of 30, there are at least 30 evaluable subjects in each treatment group, and the two-sided Wilcoxon rank sum test will be used to test each pairwise treatment difference at the 0.05 Type I error level. Under the fixed-sequence strategy which maintains an overall 0.05 Type I error rate, the study has at least 80% overall power to detect both treatment differences (i.e., both high dose versus placebo and low dose versus placebo), if each mean treatment difference is at least 24. If the study does not proceed to the high-dose level, (i.e., there are 30 evaluable subjects treated with 25 mg TVB-2640 and only 15 with placebo), then the study has at least 77% power to detect a mean treatment difference of at least 24. The study will have more power if the subjects from China are included in the primary analysis and the same assumptions of treatment difference and variability hold.

Power calculations for the key secondary endpoint (percentage of subjects with at least a 30% reduction in the primary endpoint) are based on pairwise comparisons with the placebo group using Fisher's two-sided exact test [equivalent to Cochran-Mantel-Haenszel (CMH) without stratification] at the 0.05 significance level. Based on Loomba (2018), it is expected there will be less than 5 responses out of 30 evaluable subjects in the placebo group (i.e., less than 16.7%). With 30 evaluable subjects in each treatment group, there is at least 80% power to detect at least a 36.7% increase in the response rate (TVB-2640 treatment group minus placebo) when the placebo response rate is at most 16.7%. If the study does not proceed to the high-dose level, (i.e., 30 evaluable subjects treated with 25 mg TVB-2640 and only 15 with placebo), then the study has at least 63% power to detect at least a 36.7% increase in the response rate (25 mg TVB-2640 treatment group minus placebo) when the placebo response rate is at most 2 out of 15 evaluable subjects (i.e., 13.34%). With 30 subjects in each TVB-2640 treatment arm, there is at least a 95% probability of detecting at least 1 AE when the AE rate is 10% or more in the underlying population.

3.4. Safety Review Committee

An SRC will oversee the study to ensure subject safety and to advise if any dosing alterations are recommended. The SRC will review safety including liver-related events (i.e., clinically

Sponsor: Sagimet Biosciences
Protocol Number: 3V2640-CLIN-005
Version and Date: Final Version 1, 02June2020

meaningful elevations in ALT, AST, and bilirubin), and other efficacy (lipid parameters) and safety data as needed.

If study suspension criteria are met at any time (see Protocol Section 7.2), the SRC will review the relevant study data and make a determination whether enrollment and treatment of subjects may continue or be permanently terminated. In addition, the SRC will review all safety data from the 25 mg dose level after all subjects at that dose level complete the 12-week treatment period. Enrollment and treatment of subjects at the 50 mg dose level may commence only with the written approval of the SRC and with FDA review. The SRC may also review data from the 50 mg cohort, if performed, upon request (see below).

Additional details on the SRC can be found in the SRC Plan. The SRC Plan includes details on membership, purpose, organization, data requirements, logistics, and reporting requirements.

3.5. Timing of Analyses

An interim analysis for SRC review will be performed after all of the subjects in the 25 mg dose level complete the 12-week treatment period. Details on data requirements and outputs required will be maintained in the SRC Plan or other related documents.

An additional SRC analysis was performed during the COVID pandemic to confirm safety prior to allowing the option for extended 50 mg cohort dosing.

The primary analysis of efficacy will be performed when all subjects in the US 50 mg cohort finish their final visit. The primary analysis will not include any data from China, due to delays and uncertainty of enrollment in the Chinese cohort.

An End of Study final analysis will be performed when the final subject completes the study and will include cumulative data from the US and China as applicable.

4. STUDY ENDPOINTS

4.1. Efficacy

The primary efficacy endpoint is:

- Percent change from baseline in liver fat at Week 12, as determined by MRI-PDFF.

The key secondary efficacy endpoint is:

- The percentage of subjects with at least a 30% reduction in liver fat at Week 12, as determined by MRI-PDFF.

Additional secondary efficacy endpoints are:

- Percent change from baseline in liver fat at End of Treatment and End of Study, as determined by MRI-PDFF.

Sponsor: Sagimet Biosciences

Protocol Number: 3V2640-CLIN-005

Version and Date: Final Version 1, 02June2020

- Percentage of subjects with at least a 30% reduction in liver fat at End of Treatment and End of Study, as determined by MRI-PDFF.
- Change from baseline over the treatment period in:
 - Liver aminotransferases.
 - Lipid and lipoprotein parameters.
 - NASH and fibrosis markers.
 - Eicosanoids.

Exploratory efficacy endpoints are:

- Change from baseline over the treatment period in:
 - Liver fibrosis, as determined by VCTE.
 - Metabolic parameters.
 - Anthropometric parameters.
 - Lipidomic analyses for DNL.
- Proportion of subjects with <5% liver fat (normalized) at Week 12.

4.2. Safety

Safety endpoints are:

- Proportion of subjects experiencing treatment-emergent adverse events (TEAEs), Grade 3 or 4 TEAEs, and serious adverse events (SAEs).
- Change from baseline in vital sign measurements, 12-lead ECG findings, and clinical laboratory test results.
- Proportion of subjects experiencing treatment-emergent ophthalmologic abnormalities.

5. ANALYSIS POPULATIONS/SETS

The modified intent-to-treat population (mITT) is defined as all subjects who are randomized, receive study drug for at least 8 weeks, and have a baseline and at least 1 post-baseline MRI-PDFF assessment on or after Week 8. The mITT is the primary population for analysis of MRI-PDFF assessments and subjects will be analyzed according to the randomized treatment assignment.

The intent-to-treat population (ITT) is defined as all subjects who are randomized and received at least 1 dose of study drug. The ITT will be used for analysis of a subset of secondary efficacy endpoints and supportive and sensitivity analyses of MRI-PDFF assessments. Subjects will be analyzed according to the randomized treatment assignment.

The as-treated population (ATP) is defined as all subjects who are randomized and received at least 1 dose of study drug. The ATP will be used for analysis of secondary efficacy endpoints and supportive and sensitivity analyses of MRI-PDFF assessments. Subjects will be analyzed according to the treatment received.

The safety population is defined as all subjects who are randomized and received at least 1 dose of study drug and will be used for all analysis of safety. Subjects will be analyzed according to

the treatment received. If all subjects were dosed according to randomized treatment assignment, then the safety population and ITT are identical.

A per-protocol (PP) population may be defined for sensitivity analyses of the efficacy endpoints. The PP population will be based on subjects in the mITT population with data excluded from subjects who have important protocol violations deemed to possibly affect the efficacy measurements or integrity of any other key study data. Subjects will be analyzed according to the actual treatment received. If a PP population is implemented, details on subjects excluded will be provided in the CSR.

6. DEFINITIONS

7. GENERAL DATA HANDLING CONSIDERATIONS

All analyses will be conducted using SAS® software Version 9.4 or higher.

All data in the database will be presented in by-subject data listings.

Unless otherwise stated, all listings will be sorted by treatment group, center ID, subject number, and assessment date and time, if available.

Unless stated otherwise, continuous data will be summarized by treatment group using descriptive statistics including number of subjects (n), mean, median, standard deviation (SD), first quartile (Q1), third quartile (Q3), minimum (min) value, and maximum (max) value.

Unless stated otherwise, categorical data will be summarized by treatment group using counts and percentage based on the number of non-missing values. For selected summaries, the number of missing values will be presented as a separate category with no percentage, if one or more subjects have missing data. Counts of zero will be presented without percentages.

Descriptive statistics will be presented with the following numerical precision:

- Minimum and Maximum: same as the raw data collected
- Mean, Median, Q1, and Q3: one additional decimal place to that reported for Minimum and Maximum
- SD: two additional decimal places than the Minimum and Maximum
- Percentages: reported to one decimal place if percent is <100. If the value is 100, no decimal place will be reported.

Unless otherwise noted, statistical inference will be based on 2-sided testing with a 5% significance level (i.e. 95% confidence intervals [CI] will be produced).

P-values will be reported to four decimal places. If the value is below 0.0001 it will be noted as < 0.0001; if the value above 0.9999 it will be noted as > 0.9999.

Sponsor: Sagimet Biosciences
Protocol Number: 3V2640-CLIN-005
Version and Date: Final Version 1, 02June2020

All data up to the time of study completion/withdrawal from the study will be included in the analysis, regardless of duration of treatment.

Numbering for data displays will be based on International Council for Harmonisation (ICH) E3 whenever possible.

7.1. Stratification and Covariates

At each dose level, subjects will be randomly assigned to TVB-2640 or placebo at a 2:1 ratio, with randomization stratified by type 2 diabetes mellitus status (present/absent). The 50 mg dose level will also be stratified by country (US/China) for the final analysis. Selected statistical models and tests will be stratified based on the randomization strata. Details on the models and tests are provided in the relevant sections below.

This is a multi-center trial. However, adjustment for study center will not be made in the statistical tests.

7.2. Evaluation of Subgroups

All analyses will be performed separately by country (US and China) in addition to overall.

Selected analyses of liver fat reduction may also be repeated based on the following subgroups:

- ALT: Baseline $\geq 1.5 \times$ ULN vs $< 1.5 \times$ ULN
- DM status: present vs absent
- Baseline MRI-PDFF: \geq median vs $<$ median
- Baseline MRE: \geq median vs $<$ median
- Liver stiffness based on fibrosis stage: Stage 1 vs Stage 2/3
- Baseline triglycerides: \geq median vs $<$ median
- Weight change: $\geq 5\%$ loss vs $< 5\%$ loss (or a gain)

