Note: Significant alcohol consumption is defined as average of >20 g/day in female subjects and >30 g/day in male subjects. For reference, 14 grams of alcohol are contained in the following:

- 12 fl oz regular beer containing ~5% alcohol.
 - 8-9 fl oz malt liquor containing ~7% alcohol.
 - 5 fl oz of table wine containing ~12% alcohol.
 - 1.5 fl oz of distilled spirits (e.g., gin, rum, vodka, whiskey) containing ~40% alcohol.
2. Inability to reliably quantify alcohol consumption based upon judgment of the Investigator.
 3. Use of drugs historically associated with NAFLD (amiodarone, methotrexate, systemic glucocorticoids, tetracyclines, tamoxifen, estrogens at doses greater than those used for hormone replacement, anabolic steroids, valproic acid, and other known hepatotoxins) for more than 2 weeks in the year prior to screening.
 4. Weight gain or loss >5% in the 6 months prior to randomization or >10% in the 12 months prior to screening.
 5. Prior or planned (during the study period) bariatric surgery (e.g., gastroplasty, roux-en-Y gastric bypass).
 6. Type 1 diabetes.
 7. Uncontrolled Type 2 diabetes defined as:
 - HbA1c $\geq 9.5\%$ during screening. (Subjects with HbA1c $\geq 9.5\%$ may be retested during screening).
 - Basal insulin dose adjustment >10% within 60 days prior to enrollment.
 - Requirement for glucagon-like peptide analogue or a complex oral anti-diabetic (OAD) regimen (3 or more OADs) within 6 months of screening.
 - History of severe hypoglycemia (symptomatic hypoglycemia requiring outside assistance to regain normal neurologic status) within the previous year.

Note: Individual diabetes regimens will be reviewed by Investigator and may be adjusted based on American Diabetes Association guidelines.

8. Presence of cirrhosis on liver biopsy (Stage 4 fibrosis) or imaging (MRE ≥ 4.67 kpa).
9. Platelet count $< 150 \times 10^9/L$.
10. Clinical evidence of hepatic decompensation as defined by the presence of any of the following abnormalities:
 - Serum albumin ≤ 3.5 g/dL,
 - International normalized ratio (INR) ≥ 1.3 (a single retest is permitted if laboratory error is suspected),
 - Total bilirubin > 1.8 mg/dL and/or direct bilirubin > 0.8 mg/dL (unless due to Gilbert's syndrome, as documented in the subject's medical history/records), or
 - History of esophageal varices, ascites, or hepatic encephalopathy.

11. Evidence of other forms of chronic liver disease including the following:

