Similar responder analyses will be performed using response level definitions of 20%, 40%, and 50%. As done for the key secondary endpoint efficacy endpoint, subjects with a reduction of at least 19.5%, 39.5%, and 49.5% from baseline, respectively, will count as responders. Analyses will be repeated in the ITT, ATP, and PP populations. Analyses of the key secondary endpoint performed in the ATP populations will include summaries of all subjects in the analysis population, as well as the subset of subjects that have at least 8 weeks of treatment and an evaluable assessment on/after 8 weeks (i.e., the same subjects in the mITT population).

Similar responder analyses will be performed using reduction in liver fat at End of Study in the mITT, ITT, and ATP populations.

A scatter plot of End of Treatment body weight changes versus End of Treatment liver fat changes will be graphed by treatment and overall in the ATP. A subset will also be run in subjects with at least a 30% reduction in liver fat at Week 12.

In the key secondary analysis, missing Week 12 values for MRI-PDFF will be imputed with the last post-baseline observation on or after Week 8 in the mITT population. Sensitivity analyses excluding subjects with missing data will also be performed.

Other Efficacy Endpoints

Other efficacy endpoints will be summarized using the ATP. A limited set of endpoints will be repeated in the ITT.

Liver aminotransferases will be evaluated using observed values and changes from baseline by study visit. Summaries will be performed for ALT and AST and will be presented by treatment group.

The changes at 12 weeks will be summarized for each treatment group and compared between each TVB-2640 dose group and pooled placebo using a linear mixed-effects model for repeated measures (MMRM). The model will include the stratification factor (diabetes presence/absence),

Sponsor: Sagimet Biosciences

Protocol Number: 3V2640-CLIN-005

Version and Date: Final Version 1, 02June2020

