8.3.3. Exploratory Efficacy Endpoints and Analyses

Analysis of exploratory endpoints will be based on the ATP. Exploratory efficacy endpoints include the change from baseline over the treatment period in following continuous measurements:

- Liver fibrosis, as determined by VCTE
- Metabolic parameters
- Anthropometric parameters including weight, waist and hip circumference, waist-hip ratio, and blood pressure
- Lipidomic analyses for DNL

Analyses will be performed similarly to those described in the secondary efficacy analysis section above.

The proportion of subjects with <5% liver fat (normalized) at Week 12 will be summarized by treatment group. Analyses similar to those described for the key secondary efficacy endpoint will be used.

Subset analyses will be performed on all exploratory efficacy endpoints for subjects enrolled in the US and China to evaluate the consistency of results between subjects enrolled in each country.

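### The optional liver-fat subgroup analysis by weight change (SAP 7.2) conditions on a post-randomisation variable, so treatment comparisons within it are not protected by randomisation

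*SAP*

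**What the plan says.** SAP 7.2 introduces its list with "Selected analyses of liver fat reduction may also be repeated based on the following subgroups". Baseline values define four of the items: ALT, MRI-PDFF, MRE and triglycerides. Diabetes status and fibrosis stage are also known at entry. The last item is weight change, cut at a 5% loss, with no baseline label and no time point.

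Elsewhere the SAP treats weight change as something that happens on study. Section 8.3.2 says "A scatter plot of End of Treatment body weight changes versus End of Treatment liver fat changes will be graphed by treatment and overall". Section 8.3.3 makes change over the treatment period in "Anthropometric parameters including weight, waist and hip circumference, waist-hip ratio, and blood pressure" an exploratory efficacy endpoint.

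The protocol also excludes subjects with "Weight gain or loss >5% in the 6 months prior to randomization or >10% in the 12 months prior to screening" (synopsis, repeated in section 8.3).

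SAP 7 sets a default of two-sided 5% inference with 95% confidence intervals unless something else is noted. Section 7.2 notes nothing else for this item: no caveat, no minimum cell size and no descriptive label.

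**The concern.** A subgroup fixed before randomisation keeps the randomised comparison inside it. A subgroup defined by what happens afterwards need not. If the drug changes weight, subjects on drug who lose 5% or more are a different kind of subject from those on placebo who do so. The same holds for those who stay below 5%. If weight change and liver-fat change share causes such as diet or activity, the within-stratum contrast mixes the drug effect with that imbalance.

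Independence of treatment and weight cannot be assumed here:

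- The sponsor itself analyses weight as an outcome.
- Site personnel other than imaging staff know the assignment (SAP 3.2), so advice could differ by arm.
- Protocol 5.1 reports decreased appetite in 26% of oncology monotherapy patients, though in an uncontrolled study of a different population.

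None of this shows an effect on weight. What is at stake is interpretation: a reader of such a table, set beside baseline subgroups, may take it to show whether the liver-fat effect depends on weight loss.

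**Working it through.** **Which weight change is meant.** A pre-study reading fails, because the entry criterion quoted above would leave the 5%-or-more loss group almost empty by design. SAP 8.3.2 and 8.3.3 both use change during treatment. On-study change is therefore an inference, but the only coherent one.

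**Inputs from SAP 3.3.** The US analysis is sized as "resulting in 30 evaluable subjects in the placebo group, and 30 evaluable subjects in each of the TVB-2640 dose levels". The SD of the primary endpoint is 30 points, the design difference is 24, and the test is a two-sided Wilcoxon at 0.05. The plan states no figure for these subgroups. Its overall claim of at least 80% power for both doses is reproduced under its lognormal assumption: simulation gives 80.1% (shifted lognormal) to 83.2% (equal-SD lognormal), with the placebo mean at 100% of baseline. Normal data give 74.1%. The SD and group sizes are thus usable below.

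**Cell sizes and precision.** The documents give no rate of 5% weight loss, so a range is assumed, equal in both arms. Expected size is n = 30 × rate, and the half-width is 1.96 × 30 × √(2/n).

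| Assumed rate | n per arm, loss of 5% or more | Chance of 2 or fewer on placebo | Half-width | n per arm, other stratum | Half-width |
|---|---|---|---|---|---|
| 5% | 1.5 | 81% | 68 | 28.5 | 15.6 |
| 10% | 3 | 41% | 48 | 27 | 16.0 |
| 20% | 6 | 4% | 34 | 24 | 17.0 |
| 30% | 9 | 0.2% | 28 | 21 | 18.1 |

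The full sample gives 1.96 × 30 × √(2/30) = 15.2. The table treats the SD as known. A t interval is wider in small cells: 68 points at 3 per arm and 129 at 2 per arm.

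**Bias.** All inputs in this step except the SD of 30 are assumptions. Percent weight change is normal with SD 3 and mean -0.5 on placebo, and the drug lowers the mean by a further s points. Weight and fat residuals correlate at r through shared causes, and the true fat effect is the same in everyone. With φ and Φ the standard normal density and distribution function, put a = (-5 - mean)/3.

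- Mean standardised weight residual, loss of 5% or more: -φ(a)/Φ(a).
- Mean standardised weight residual, other stratum: φ(a)/(1 - Φ(a)).
- Bias = 30 × r × (active value minus placebo value).

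For s = 1, a is -1.5 on placebo and -1.167 on drug.

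- Loss of 5% or more: placebo -0.1295/0.0668 = -1.939; drug -0.2020/0.1217 = -1.660. At r = 0.4, the bias is 30 × 0.4 × 0.2785 = 3.3 points.
- Other stratum: 0.1295/0.9332 = 0.139 and 0.2020/0.8783 = 0.230, so 30 × 0.4 × 0.0912 = 1.1 points.

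The same formula gives:

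| s | r | Bias, loss of 5% or more | Bias, other stratum |
|---|---|---|---|
| 0 | any | 0 | 0 |
| 1 | 0.3 | 2.5 | 0.8 |
| 1 | 0.4 | 3.3 | 1.1 |
| 1 | 0.6 | 5.0 | 1.6 |
| 2 | 0.3 | 4.9 | 1.9 |
| 2 | 0.4 | 6.5 | 2.6 |
| 2 | 0.6 | 9.8 | 3.9 |

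Simulation with a true effect of -24 agrees. At s = 1 and r = 0.4 the two strata show -20.6 and -22.9; at s = 2 and r = 0.6 they show -14.1 and -20.2. Positive bias makes the drug look worse. If the drug instead raised weight by 1 point (r = 0.4), the simulated estimates are -27.3 and -24.7.

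**The case against.** The strongest reply is that little hangs on this. The wording is permissive and covers selected analyses only, and the item lies outside the fixed sequence in SAP 7.3. No passage reports a drug effect on weight, and without one the bias vanishes. In the larger stratum the illustrative bias is 1 to 4 points against a half-width of 15 to 18. All of that stands, and it limits the point to exploratory interpretation. It does not make the item equivalent to its neighbours on the list, because the table cannot show whether the no-bias condition holds.

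Three stronger readings are tempting, and the documents do not support them:

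- *The plan commits to this analysis.* It does not; the text says it may be done.
- *Both subgroups would be nearly empty.* With no weight-loss rate in the documents, this can be said only of the 5%-or-more stratum, and only if the rate is about 10% or less. The other stratum keeps 21 to 28.5 of 30 per arm over the range in the table.
- *The analysis would manufacture a finding that the drug works regardless of weight loss.* Neither document plans that claim. If the drug lowers weight and the correlation is positive, the bias runs against the drug in both strata.

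**Conclusion.** The concern holds as a minor point about one optional item. The weight-change split is the only listed subgroup that is not an entry characteristic, and treatment comparisons within it are not protected by randomisation.

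Under the stated assumptions the bias is about 2.5 to 10 points in the 5%-or-more loss stratum and 1 to 4 points in the other. It is zero if the drug has no effect on weight. Even at a 30% loss rate, the interval in the smaller stratum (about ±28 points) is wider than the design difference of 24. Excluding extended-dosing subjects (SAP 8.3.1.1) would shrink the cells further; adding the 18 active and 9 placebo subjects planned for China would enlarge them slightly.

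The conclusion rests on reading weight change as on-study, which the SAP does not state outright. Primary and key secondary inference is not affected.

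**What to change.** Delete weight change from the SAP 7.2 list. Alternatively, keep it with a stated time point and a label that it is post-randomisation and descriptive, with no between-arm p-values and no treatment-effect claims. In either case, let the weight-fat scatter plot by treatment in 8.3.2 carry the question.

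This is a one-line edit and needs no new data. The cost is one optional exploratory contrast. A substitute such as baseline BMI is not needed: it asks whether body size at entry modifies the effect, which is a different question.
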